2.1 Study Rationale

Systemic amyloidosis is an incurable disease, and about 20% of patients with cardiac or advanced kidney involvement experience early deaths (<1 year). Recent progress in the treatment of AL amyloidosis with proteasome inhibitors, chemotherapies, and immunotherapies that target plasma cells has greatly improved patient prognosis; however, median survival remains low at approximately five years (Milani 2018; Palladini 2020). Earlier quantitative detection of amyloid in abdominothoracic organs or tissues and assessment of response to treatment may improve the prognosis of these patients. However, there currently are no approved imaging agents that specifically detect and quantify amyloid deposits in patients.

As a PET/X-ray CT imaging agent that binds many forms of human and murine amyloid, ¹²⁴I-AT-01 may fulfill this unmet clinical need by enabling detection of amyloid in abdominothoracic organs or tissues of patients with systemic amyloidosis. Thus, this study has been designed to assess the repeatability of organ-specific quantitation of radiotracer uptake following PET/CT imaging of AT-01 in subjects with amyloid light chain (AL) or amyloid transthyretin (ATTR) systemic amyloidosis. This will help to determine whether AT-01 can be used to monitor disease progression and treatment response in patients with systemic amyloidosis.

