3.0 OBJECTIVES AND ENDPOINTS

| Objective | Endpoint | | |
|---|--|--|--|
| Primary | | | |
| To evaluate the repeatability of organ-specific quantitation of radiotracer uptake following PET/CT imaging of ¹²⁴ I-AT-01 in subjects with AL or ATTR systemic amyloidosis. | Repeatability coefficient (Bland-Altman plots) and ICC associated with the quantification of radioactivity associated with organ level 124I-AT-01 uptake measurements. | | |
| Secondary | | | |
| To characterize the safety and tolerability of repeat doses of ¹²⁴ I-AT-01 administered by IV infusion or slow IV bolus. | Incidence of treatment-emergent AEs¹ from Day 1 to EOS. | | |
| | Change from Baseline in clinical laboratory values ² at Visits 2 and Safety Follow-up 1 (1-3 days after the second administration of ¹²⁴ I-AT-01). | | |
| | Change from Baseline in vital signs. | | |
| | Change from Baseline in ADA. | | |

Abbreviations: ADA = anti-drug antibodies; AEs = adverse events; AL = amyloid light chain; ATTR = amyloid transthyretin; CT = computerized tomography; EOS = end of study; ICC = intraclass correlation coefficient; IV = intravenous; PET = positron emission tomography.

- 1. Adverse events will be graded using National Cancer Institute Common Terminology Criteria for Adverse Events (CTCAE) version 5.
- 2. Clinical laboratory tests are described in Section 10.2 and include hematology and serum chemistry.

- 21 -

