9.4 Analysis Sets

Safety analyses will be performed on the All-enrolled Population, consisting of all subjects who undergo at least one PET/CT scan or receive any amount of ¹²⁴I-AT-01.

Analyses of repeatability will be performed on the Image Evaluable Population, consisting of all subjects who undergo PET/CT scans on both Day 1 and 6 to 8 weeks after Day 1 and who have evaluable images at both time points.

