9.5.1 General Considerations

This is an open-label, single arm study. In general, for continuous variables, the mean, standard deviation (SD), median, and range will be presented. Categorical variables will be summarized by frequency counts and percentages.

Subject disposition will be summarized for all subjects who signed the ICF and will include the number of subjects who received study treatment and the number and percentage of subjects who completed or prematurely discontinued the study, classified by reasons for premature discontinuation.

Discontinuations

The reason for study discontinuation and the number of days post-study drug treatment on which the subject discontinued will be summarized.

Protocol Deviations

Protocol deviations will be provided in a listing with reasons for the deviation and the date of occurrence. Any exclusion of subjects from exploratory analysis populations, and how these exclusions impact data analysis, will be addressed in the clinical study report.

Missing Data

There will be no imputation for missing safety or whole blood radioactivity data.

9.5.2 **Primary Endpoint(s)**

The primary objective of this study is to evaluate the repeatability of organ-specific quantitation of radiotracer uptake following PET/CT imaging of AT-01 in subjects with AL or ATTR systemic amyloidosis. The corresponding primary endpoint is:

 Repeatability coefficient (Bland-Altman plots) and intraclass correlation coefficient (ICC) associated with the quantification of radioactivity associated with organ level ¹²⁴I-AT-01 uptake measurements.

The signal to noise ratio (SNR) and contrast to noise ratio (CNR) will be plotted against standardized uptake value (SUV) based metrics. Repeatability will be assessed using Bland-Altman plots. ICC and its associated 95% confidence interval will be presented. Quantitative organ uptake analyzed by an automated method will be summarized. Between-reader agreement in visual determination of AT-01 uptake will be evaluated by Cohen's kappa.

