8.2.3 Intraclass Correlation Coefficient (ICC)

• Computation of the Endpoint

A two-way mixed effects model with absolute agreement type for a single rater/measurement will be used to calculate the intraclass correlation coefficient. SAS Proc Mixed with subject as a random effect will be used to produce covariance parameter estimates.

ICC will be calculated as the covariance parameter estimate for subject divided by the sum of the covariance parameter estimates for subject and residuals.

Fisher's z-transformation will be used to calculate a 95% CI of ICC (r) where

$$z' = \frac{1}{2} \ln \frac{1+r}{1-r}$$
, and $SE_{z'} = \frac{1}{\sqrt{N-3}}$, making the 95% CI = $z' \pm 1.96$ SE_{z'}

To transform the endpoints of the CI back to correlation coefficients, the following formula will be used: $=\frac{\exp(2z)-1}{\exp(2z)+1}$.

• Analysis of the Endpoint

A summary table with the ICC for SUVpeak and SUVmax by organ will be produced "Among Reader by Visit": where m_1 is the average of the 2 reads for a specific reader and visit, m_2 is the average of the 2 reads for the second reader and m_3 is the average of the 2 reads for the third reader for the same visit.

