15 ATTACHMENTS

15.1 Table of Contents for Data Display Specifications

Tables		
Number	Title	Population
14.1.1	Summary of Subject Disposition	All Subjects
14.1.2.1	Summary of Subject Demographics and Baseline Characteristics	Safety
14.1.3.1	Medical History by System Organ Class and Preferred Term	Safety
14.1.3.2	Surgical or Procedural History by System Organ Class and Preferred Term	Safety
14.1.4.1	Summary of Prior Medications by Drug Class and Preferred Term	Safety
14.1.4.2	Summary of Concomitant Medications by Drug Class and Preferred Term	Safety
14.1.4.3	Summary of Prior Medications for the Treatment of Systemic Amyloidosis by Drug Class and Preferred Term	Safety
14.1.4.4	Summary of Concomitant Medications for the Treatment of Systemic Amyloidosis by Drug Class and Preferred Term	Safety
14.1.5	Summary of Protocol Deviations	Enrolled
14.1.6	Summary of Treatment Exposure	Safety
14.2.1.1.1	Within Reader Repeatability Coefficients by Reader, Visit, and SUV Metric by Organ	Image Evaluable Set
14.2.1.1.2	Within Reader Repeatability Coefficients by Reader, Visit, and SUV Metric by Organ and Amyloid Type	Image Evaluable Set

Page 33 of 38

14.2.1.2.1	Between Visit Repeatability Coefficients by Reader and SUV Metric by Organ	Image Evaluable Set
14.2.1.2.2	Between Visit Repeatability Coefficients by Reader and SUV Metric by Organ and Amyloid Type	Image Evaluable Set
14.2.1.3	Summary of Repeatability Analysis Results	Image Evaluable Set
14.2.2.1	Among Reader Intraclass Correlation Coefficients by Visit and SUV Metric by Organ	Image Evaluable Set
14.2.2.2	Among Reader Intraclass Correlation Coefficients by Visit and SUV Metric by Organ and Amyloid Type	Image Evaluable Set
14.2.3.1	Summary of Inter-rater Agreement by Visit by Organ	Image Evaluable Set
14.2.3.2	Summary of Intra-rater Agreement by Expert Radiologist by Organ	Image Evaluable Set
14.2.4	Coefficients of Variation by Visit by Organ	Image Evaluable Set
14.3.1.1	Overall Summary of Treatment-Emergent Adverse Events	Safety
14.3.1.2	Treatment-Emergent Adverse Events by System Organ Class and Preferred Term	Safety
14.3.1.3	Treatment-Emergent Adverse Events by System Organ Class, Preferred Term, and CTCAE Grade	Safety
14.3.1.4.1	Treatment-Emergent Adverse Events by System Organ Class, Preferred Term, and Relationship to AT-01	Safety
14.3.1.4.2	Treatment-Emergent Adverse Events by System Organ Class, Preferred Term, and Relationship to KI	Safety

Page **34** of **38**

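### The ICC in the primary endpoint compares three readers of the same scan, never Day 1 with Week 6, so it does not measure scan-to-scan repeatability and can rise as that repeatability worsens

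*SAP*

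**What the plan says.** The primary objective in Protocol 3.0 is "To evaluate the repeatability of organ-specific quantitation of radiotracer uptake following PET/CT imaging of" the tracer in AL or ATTR amyloidosis. The matching endpoint is "Repeatability coefficient (Bland-Altman plots) and ICC associated with the quantification of radioactivity associated with organ level" uptake. Protocol 9.5.2 adds: "Repeatability will be assessed using Bland-Altman plots. ICC and its associated 95% confidence interval will be presented". Protocol 9.4 makes the second scan a condition of entry to the analysis: "Analyses of repeatability will be performed on the Image Evaluable Population, consisting of all subjects who undergo PET/CT scans on both Day 1 and" again 6 to 8 weeks later. Protocol 2.1 gives the purpose: "This will help to determine whether AT-01 can be used to monitor disease progression and treatment response in patients with systemic amyloidosis".

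SAP 8.2.3 specifies the ICC in one way. The table "will be produced 'Among Reader by Visit': where m_1 is the average of the 2 reads for a specific reader and visit", and m2 and m3 are the corresponding averages for the second and third readers at that visit. The estimator is stated as follows: "ICC will be calculated as the covariance parameter estimate for subject divided by the sum of the covariance parameter estimates for subject and residuals".

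The display list in SAP 15.1 agrees with this. Table 14.2.2.1 is "Among Reader Intraclass Correlation Coefficients by Visit and SUV Metric by Organ", and Table 14.2.2.2 is the same by amyloid type. SAP 8.3 only repeats that ICC by amyloid type.

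The other primary methods are treated differently. SAP 8.2.1 (observed and log scale) and SAP 8.2.2 each include a comparison of Visit 1 with Visit 2 for the same reader. SAP section 2 gives the SAP precedence over the protocol, and SAP section 12 declares no changes from the protocol's analyses.

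**The concern.** Two scans per subject are acquired so that repeat measurements can be compared. An ICC computed within one visit never uses the pairing of the two scans, so it cannot say whether the second scan reproduces the first. It says how closely three readers agree on one set of images, which is reader reproducibility.

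The SAP keeps the two ideas apart elsewhere. For visual reads, section 8.2.5 treats agreement among the three experts at a visit as inter-rater agreement and analyses Scan 1 against Scan 2 separately. By that usage the planned ICC is an inter-rater statistic.

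At stake is how a named primary statistic will be read. Monitoring progression or treatment response means comparing scans over time. A value near 1, reported under a repeatability endpoint, would be taken as support for that use even if the two scans disagreed badly. The ICC is also the only quantitative uptake statistic in SAP 8.2 with a planned confidence interval. The one measure reported with its uncertainty would therefore be the one that ignores the pairing of scans.

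**Working it through.** The documents state no ICC value and no variance components, so there is no figure to reproduce. The check applies the SAP's own estimator to a simple model, with assumed variances shown over a range.

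**Model.** For one organ and one SUV metric, a reader's average of two reads is the sum of:
- a subject effect, variance B;
- a scan-day effect specific to that subject and visit, variance S (the test-retest variation);
- reader error, variance E.

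**What each ICC estimates**
- Among readers within a visit (SAP 8.2.3): all three readers see the same scan, so S is common to them and cannot be separated from B. ICC = (B + S) / (B + S + E).
- Between visits, same reader: only B is common to the two measurements. ICC = B / (B + S + E).

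The derivative of the first with respect to S is E / (B + S + E)², which is positive whenever E > 0. With reader error held fixed, the planned ICC rises as scan-to-scan variation grows.

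**Illustration on the log-SUV scale.** Assumed between-subject SD 0.5 (B = 0.25) and reader SD 0.05 (E = 0.0025).

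| Scan SD | S | Planned among-reader ICC | Between-visit ICC |
|---|---|---|---|
| 0 | 0 | 0.2500/0.2525 = 0.990 | 0.25/0.2525 = 0.990 |
| 0.1 | 0.01 | 0.2600/0.2625 = 0.990 | 0.25/0.2625 = 0.952 |
| 0.2 | 0.04 | 0.2900/0.2925 = 0.991 | 0.25/0.2925 = 0.855 |
| 0.3 | 0.09 | 0.3400/0.3425 = 0.993 | 0.25/0.3425 = 0.730 |
| 0.5 | 0.25 | 0.5000/0.5025 = 0.995 | 0.25/0.5025 = 0.498 |

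**Range over reader error.** With B = 1 and S running from 0 to 2:

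| E | Among-reader ICC | Between-visit ICC |
|---|---|---|
| 0.02 | 0.980 to 0.993 | 0.980 to 0.331 |
| 0.05 | 0.952 to 0.984 | 0.952 to 0.328 |
| 0.10 | 0.909 to 0.968 | 0.909 to 0.323 |

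Simulation (20 subjects, 3 readers, 2 visits, 4,000 runs per setting) agreed with these formulas to within about 0.025. In the limiting case B = 0, S = 1, E = 0.05, where scans carry no stable subject signal, the planned ICC is 1/1.05 = 0.952 and the between-visit ICC is 0.

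**Checks that do not depend on the variances.** The per-visit ICC cannot change if Week 6 values are reassigned among subjects, or if all Week 6 values move by a constant. One simulated dataset shows the effect:
- Shuffling Week 6 across subjects left the two per-visit ICCs at 0.948 and 0.946, while the between-visit ICC fell from 0.956 to 0.265.
- Lowering every Week 6 value by two between-subject SDs left the Week 6 ICC at 0.946, while the between-visit ICC fell to about −0.01.

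**The case against.** The strongest reply is that the between-visit question is already answered elsewhere. SAP 8.2.1 gives a between-visit repeatability coefficient on both scales and a within-subject CV, and SAP 8.2.2 gives between-visit Bland-Altman plots. In the illustration above, SD(d) = √(2(S + E)). The planned log-scale limits, (exp(±1.96 × SD(d)) − 1) × 100, would then read:
- scan SD 0.2: SD(d) = √0.085 = 0.292, limits +77% and −44%, wCV 23%;
- scan SD 0.3: SD(d) = √0.185 = 0.430, limits +132% and −57%, wCV 36%;
- scan SD 0.5: SD(d) = √0.505 = 0.711, limits +303% and −75%, wCV 65%.

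Poor repeatability would be visible. That stands, and it limits the damage to the ICC component.

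Other points also have weight. The protocol does not say which comparison the ICC should make. SAP 8.2 says its methods cover several types of repeatability, so an among-reader ICC is a legitimate addition. The tables are titled as among-reader. There is no hypothesis, and no decision rule rests on the ICC. The rise in the planned ICC is slight and assumes that reader error does not grow with scan variation. For monitoring an individual patient, the repeatability coefficient and wCV are more directly useful than any ICC.

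None of this supplies a between-visit ICC. The contents of Table 14.2.1.3, a summary of repeatability results, are not spelled out, but no text defines such an ICC for it. An accurate table title does not turn inter-reader agreement into the repeatability statistic that the endpoint promises.

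**Conclusion.** The concern holds. Followed exactly, the SAP would report inter-reader agreement as the ICC for a scan-to-scan repeatability endpoint. This is wrong as written, not merely short of detail. The planned ICC is insensitive to disagreement between the scans and, with reader error fixed, moves slightly in the wrong direction: 0.990 to 0.995 in the illustration, while the between-visit ICC goes from 0.990 to 0.498.

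Those magnitudes rest on assumed variances and on a log scale that SAP 8.2.3 does not specify for the ICC. A scan SD equal to the between-subject SD is the far end of the range shown. The structural result, that scan-day variance enters the numerator and the pairing of scans is never used, does not depend on those values. The between-visit repeatability coefficient, wCV and Bland-Altman plots are unaffected and still address the primary question.

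**What to change.** - In SAP 8.2.3, add a between-visit ICC by reader for each organ and SUV metric, with m1 the reader's Visit 1 average and m2 the same reader's Visit 2 average, as already defined in 8.2.1 and 8.2.2. Keep the absolute-agreement form, so that a mean shift between visits counts against agreement.
- Name this as the primary-endpoint ICC, and relabel the among-reader ICC as inter-reader reproducibility.
- Carry it into the amyloid-type subgroup analysis in 8.3, and add matching tables beside 14.2.2.1 and 14.2.2.2.
- Optionally, fit one mixed model with subject, subject-by-visit, reader and residual variances, which gives both ICCs from a single analysis.

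The cost is some SAP wording and one or two extra tables from data already collected. The between-visit ICC will probably be lower than the among-reader value.

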8.2.4 Signal to Noise and Contrast to Noise Ratios

• Computation of the Endpoint

SNR is calculated as (suv peak organ / suv peak organ std dev) for each read.

CNR is calculated as ([suv_peak_organ]-[suv_peak_aorta_cylinder]) / (suv_peak_aorta_std_dev_cylinder) for each read.

Page 19 of 38

Version Date: 2022-12-16 Version: 2.0

Document Control No.: TMP-SA-008-01 Template Effective Date: 23 Mar 2021

All variables come from the imaging dataset.

• Analysis of the Endpoint

Signal to Noise ratios (SNR) and Contrast to Noise ratios (CNR) will each be plotted against SUVpeak and SUVmax by organ for the Image Evaluable Set by reader (taking the averages of the two reads) and visit.

8.2.5 Inter-rater and Intra-rater Agreement

AT-01 uptake is determined by three expert radiologists determination of AT-01 uptake for each region, it is one evaluation per expert per organ per visit. The number and % of subjects with positive AT-01 uptake will be described by expert by visit and organ. The inter-rater agreement in positive AT-01 uptake between the three expert radiologist's determination by visit will be presented using Fleiss' kappa. The intra-rater agreement in positive AT-01 uptake between Scan 1 and Scan 2 in each expert radiologist's determination by expert will be presented using Cohen's kappa and its 95% confidence interval.

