4.1.3 Administration Period

Administration of ¹²⁴I-AT-01 and the associated study procedures occur at the Day 1 and Week 6 (+ 2 week) visits. Administration of ¹²⁴I-AT-01 and the associated study procedures are described in Section 4.1.3.1.

4.1.3.1 Administration of Study Intervention(s) and Associated Procedures Day 1 and Week 6 (+ 2 week) Visits

The schedule for administration of ¹²⁴I-AT-01 is provided in the SoA (Section 1.3). Administration of ¹²⁴I-AT-01 occurs at the Day 1 and Week 6 to Week 8 visits, as follows:

Prior to Administration of ¹²⁴I-AT-01

- 1) Clinical laboratory tests and biomarker analysis (including serum pregnancy test in WOCBP) will be obtained within 7 days prior to the second administration of ¹²⁴I-AT-01, as described in the SoA (Section 1.3). The results of the pregnancy test must be available and be negative prior to ¹²⁴I-AT-01 administration in all WOCBP.
- 2) Instruct subject to take oral KI daily for 3 days, as described in Section 4.1.2.
- 3) Record concomitant medications and monitor and record AEs throughout the study visit.

Administration of ¹²⁴I-AT-01

4) Subjects enrolled under protocol Version 2.0 will receive a single dose of 1 mCi (± 10%) 124I-AT-01 by slow IV bolus at a rate of 1 mL/ 5 seconds. During 124I-AT-01 administration, monitor subjects for infusion-related reactions (IRRs), as described in Section 7.1.1. For all subjects, 124I-AT-01 will be administered by the same route (IV infusion over 2-5 minutes or slow IV bolus at 1 mL/5 seconds) at the Week 6 visit as on the Day 1 visit.

After Completion of Administration of ¹²⁴I-AT-01

- 5) Blood pressure and heart rate will be measured 5-10 minutes after administration of ¹²⁴I-AT-01.
- 6) Subjects will undergo a PET/CT scan 5 hours (± 30 minutes) after the start of administration of ¹²⁴I-AT-01 to quantify ¹²⁴I-AT-01 uptake in organs. ¹²⁴I-AT-01 whole-body scans will be acquired by study-designated PET/CT scanners, as described in Section 8.1.4.
 - Subjects will be discontinued if amyloid deposits are not identified in the Day 1 PET/CT scan in at least one of the following organs: heart, liver, spleen or kidney (i.e., they will not receive a second administration of ¹²⁴I-AT-01 or undergo a second scan) and will undergo early termination (ET) activities, as provided in the SoA (Section 1.3) and as described in Section 4.1.5.
- 7) Any adverse events will be recorded; patient can be discharged after completing the scan and deemed stable by study staff.

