9.3 Sample Size Determination

A formal sample size calculation is not provided for this study. The sample size of up to 20 subjects was estimated based on systematic literature review analysis sets.

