3.3 Study Design

This is a multicenter, open-label, single arm study in subjects with AL or ATTR systemic amyloidosis. ¹²⁴I-AT-01 is the only study intervention; neither reference therapy nor placebo will be administered.

This study consists of a screening period of up to 30 days; two, one-day treatment periods (Day 1 and Week 6); a safety follow-up 1-3 days after the second administration of 124 I-AT-01, and a final safety follow-up 28 ± 3 days after the second administration of 124 I-AT-01. Thus, the total subject duration is approximately 14 weeks. A study flow chart is provided in appendix 14.1 and a schedule of events is provided in appendix 14.2.

A formal sample size calculation is not provided for this study. The sample size of up to 20 subjects was estimated based on systematic literature review analysis sets.

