8.2 Primary Endpoint

The repeatability of organ-specific quantitation of radiotracer uptake will be assessed using PET/CT imaging of ¹²⁴I-AT-01 in subjects with AL or ATTR systemic amyloidosis and will be presented using multiple methods by organ (heart, liver, spleen, and kidney) to explain the relationship and describe the variability between assessments. The quantitative methods that will be used are (1) repeatability coefficients, (2) Bland-Altman plots, (3) Intraclass Correlation Coefficients (ICC), and (4) Signal-to-Noise Ratio and Contrast-to-Noise Ratio vs SUV-based metrics plots. There are 3 readers at each time point and 2 reads per scan per reader for quantitative reads. The above quantitative methods will be deployed to measure multiple types of repeatability.

These methods are described in more detail in sections 8.2.1, 8.2.2, 8.2.3, and 8.2.4.

The SUV-based metrics are peak SUV (denoted SUVpeak, collected as suv_peak_organ from the imaging dataset), and max SUV (denoted SUVmax, collected as suv_max_organ from the imaging dataset).

In addition to the above quantitative methods, AT-01 uptake will be visually determined by three expert radiologists for each scan of each organ. Agreement among the three reads will be evaluated by scan using Fleiss' kappa. Agreement between each reader's two scans will be evaluated using Cohen's kappa. Details are described in section 8.2.5.

The quality of imaging results will be taken into consideration such that any images with a "Not Readable" indication of scan image quality will be excluded from primary analyses.

All imaging results will be listed.

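### Visual agreement is summarised by kappa alone, by organ in at most 20 subjects; if an organ is almost uniformly positive or negative, kappa and its interval can fail despite 90-100% agreement

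*SAP*

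**What the plan says.** SAP 8.2 places the visual reads alongside the quantitative measures: "Agreement among the three reads will be evaluated by scan using" Fleiss' kappa, and each reader's two scans are compared with Cohen's kappa. SAP 8.2.5 adds the detail. There are three experts, and "it is one evaluation per expert per organ per visit". The inter-rater "determination by visit will be presented using Fleiss' kappa", with no interval mentioned. For "The intra-rater agreement in positive AT-01 uptake between Scan 1 and Scan 2", each radiologist's "determination by expert will be presented using Cohen's kappa and its 95% confidence interval". The only other visual summary in that section is the count and percentage of positive subjects by expert, visit and organ.

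The SAP table list (15.1) shows that both kappas are produced by organ in the Image Evaluable Set: Table 14.2.3.1 for inter-rater and Table 14.2.3.2 for intra-rater agreement. No observed agreement, no positive or negative agreement, and no rule for a kappa that cannot be computed appears in the SAP.

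On numbers, SAP 3.3 states "A formal sample size calculation is not provided for this study", and Protocol 9.3 says "The sample size of up to 20 subjects was estimated based on systematic literature review analysis sets" (the synopsis says approximately 20). On selection, Protocol 4.1.3.1 says "Subjects will be discontinued if amyloid deposits are not identified in the Day 1 PET/CT scan" in at least one of heart, liver, spleen or kidney. Such subjects have no second scan and cannot enter the Image Evaluable Set.

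**The concern.** Kappa measures agreement beyond chance, and the chance term depends on how many reads are positive. When nearly every read in an organ is positive (or nearly every read negative), chance agreement approaches 100%. Kappa then becomes a ratio of two very small numbers, and one or two discordant subjects decide its value.

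Protocol 5.1 makes this plausible for the heart. An ATTR subject needs either a positive cardiac biopsy or two of three criteria, and two of those three (septal wall thickness and myocardial uptake on PYP scintigraphy) are cardiac. Any pair therefore includes a cardiac one. No ATTR criterion requires liver, spleen or kidney involvement, so reads there could lean negative if the sample is mostly ATTR.

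At stake is how the visual result reads in the study report. An organ with almost perfect agreement could be shown as having no agreement beyond chance, or as having no result.

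**Working it through.** The documents state no kappa target or precision figure, so there is nothing of the plan's own to reproduce.

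**Inputs.** From the documents: n = 20 as the planned upper figure; three experts; one positive/negative evaluation per expert, organ and visit. Not given, so assumed: organ-level positivity (20% to 100%) and accuracy of a single read (95% or 98%, reads independent given true status).

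**Cohen's kappa, scan 1 against scan 2.** Write the table as (both positive, positive then negative, negative then positive, both negative). Kappa = (Po − Pe)/(1 − Pe), where Po is observed agreement and Pe is chance agreement from the margins. The SAP names no variance formula; the intervals use the standard large-sample one.

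| Table, n = 20 | Po | Pe | Kappa | Large-sample 95% CI | Exact 95% CI for agreement |
|---|---|---|---|---|---|
| (20,0,0,0) | 100% | 1.000 | 0/0, undefined | none | 83.2-100% |
| (19,1,0,0) | 95% | 0.950 | 0.00 | 0 to 0 | 75.1-99.9% |
| (18,2,0,0) | 90% | 0.900 | 0.00 | 0 to 0 | 68.3-98.8% |
| (18,1,1,0) | 90% | 0.905 | −0.053 | −0.125 to 0.020 | 68.3-98.8% |
| (9,1,1,9) | 90% | 0.500 | 0.80 | 0.537 to 1.063 | 68.3-98.8% |

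Example, row 4: Pe = 0.95² + 0.05² = 0.905, so kappa = (0.900 − 0.905)/0.095 = −0.053. The last row has the same 90% agreement with balanced margins.

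Rows 2 and 3 show a general feature. If one scan is positive in every subject, Po equals Pe and kappa is exactly 0. For row 2 the bracketed part of the variance is 0.95 × (1 − 1.95)² + 0.05 × 0.95² − 0.95² = 0.857375 + 0.045125 − 0.9025 = 0. The interval therefore has zero width, although one discordant subject in 20 is far from certainty.

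By symmetry the same happens near 0% positive: (0,1,1,18) also gives −0.053.

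**Fleiss' kappa, three readers.**
- All 20 subjects unanimously positive: undefined.
- One subject split 2-1, the rest all positive: pairwise agreement = (19 + 1/3)/20 = 96.7%; positive share = 59/60; Pe = 0.9672; kappa = −0.017.
- Two split: pairwise agreement 93.3%, Pe = 0.9356, kappa = −0.034.

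**How often.** Simulating 40,000 trials per setting with n = 20 under the assumptions above gives the probability that Cohen's kappa is undefined or at most 0 when observed agreement is at least 90%:

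| Organ positivity | 95% read accuracy | 98% read accuracy |
|---|---|---|
| 100% | 0.95 | 0.99 |
| 95% | 0.37 | 0.37 |
| 90% | 0.13 | 0.13 |
| 80% | 0.01 | 0.01 |
| 50% | about 0 | about 0 |
| 20% | 0.01 | 0.01 |

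At 95% read accuracy, mean agreement is 90.5% at every positivity rate, yet median kappa falls from 0.80 at 50% positive to 0.62 at 90% and 0.44 at 95%.

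**What the planned percent positive adds.** Alone it does not fix agreement: 18/20 positive on both scans fits 80%, 90% or 100% agreement. The corresponding kappas are −0.11, 0.44 and 1.00, so margins and kappa together do fix it through Po = kappa × (1 − Pe) + Pe. For kappa 0.444 and Pe = 0.82, Po = 0.444 × 0.18 + 0.82 = 0.90.

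**The case against.** The strongest reply is that little is missing. Given complete pairs, each expert's two percentages plus Cohen's kappa determine the 2x2 table. Where kappa is undefined, both margins are 100% (or both 0%) and agreement must be 100%. The same holds for Fleiss' kappa, whose chance term comes from the average of the three percentages. All imaging results are also listed (Listing 16.2.6). This stands for the point estimate. It does not supply an interval: the reader would have to rebuild the table and calculate one by hand, because the planned kappa interval is degenerate in some of these cases and Fleiss' kappa has none.

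A reader might infer that the set is selected for positive uptake and that organs will therefore be nearly all positive. The documents do not support this. The Day 1 rule works at subject level, requiring one of four organs, and the Protocol does not say whose read applies it. The rate above 90% in Protocol 2.2.2 is for one or more organs. AL subjects can qualify on renal or liver evidence, and no AL/ATTR mix is fixed. The restriction in SAP 8.2.1.2 to organs positive by all three experts is written for the repeatability coefficients, not for these kappas.

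It is also fair that table specifications are separate documents (SAP 2), so the shells may already carry agreement counts. The SAP text does not plan them.

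**Conclusion.** The point holds as a reporting weakness that can arise, not one that must. It matters for any organ with about 90% or more positive reads, or 10% or less; under the stated assumptions it is negligible between 20% and 80%. Near-uniform reads are plausible for the heart but are not established by the documents. Where they occur, kappa can be at or below zero, or undefined, with 90-100% agreement, and the Cohen interval can shrink to a single value of 0.

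A reader might also infer that the primary endpoint is compromised. It is not. The visual reads are additional to the quantitative measures, the repeatability coefficient and ICC do not use kappa, and there is no hypothesis or kappa threshold to fail. Nor is a comparison of kappas between organs planned. This is a low-cost improvement worth settling before database lock, so that the statistic is not chosen after the reads are seen.

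**What to change.** In SAP 8.2.5 and Tables 14.2.3.1 and 14.2.3.2:

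- Beside each Cohen's kappa, report observed scan 1 versus scan 2 agreement with an exact 95% confidence interval, for each expert and organ.
- Beside each Fleiss' kappa, report the proportion of subjects with unanimous reads, with an exact 95% interval. Counting subjects rather than reader pairs keeps the units independent.
- Add positive and negative agreement. For (18,1,1,0), positive agreement is 36/38 = 94.7% and negative agreement is 0/2 = 0%, which shows where the disagreement lies. Mark either as not applicable when its denominator is zero.
- Give a 95% interval for Fleiss' kappa where it can be estimated, and name the method.
- State that observed agreement is the reported result for an organ when kappa or its interval cannot be computed or is degenerate.

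The cost is a few cells in two tables and a few sentences in the SAP. No new reads or data are needed.
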